8.3.2 Present therapeutic situation

The most effective radiochemotherapy regimens, containing 5-FU and cisplatin, achieve a overall survival (OS) rate of 36% to 40% after two years [49, 50, 52]. Thus, a 40% OS rate at 2 years is assumed as the baseline efficacy level for the present trial.

8.3.3 Rationale for the application of a randomized phase II design

The present trial is designed as a randomized phase II study which aims at estimating the therapeutic efficacy of the experimental targeted regimen including the EGFR antibody in relation to the standard combination. The OS rate after 2 years is chosen as primary efficacy endpoint.

The estimation of the efficacy rate of the experimental cetuximab regimen is to be based on an explorative pilot study, since immediate embarking on a large scale comparative efficacy trial would not be acceptable from the point of view of resources. Moreover, this would induce ethical objections, as it does not seem to be justifiable to expose a large number of patients to an experimental approach without any exploratory indications of an improved risk-benefit ratio.

In this situation, a randomized phase II trial with a standard treatment control group proves to be an appropriate research design in order to achieve a valid efficacy estimation. This type of cancer study design is propagated since the early 1980s, especially by representatives of the National Cancer Institute [48]. The key idea of randomizing already in the phase II of the treatment development offers the opportunity to reduce some of the result variability which is typically encountered in phase II trials, especially caused by patient selection phenomena and investigator bias. Thus, with a randomized control group at hand, differences obtained for the two treatments will more likely represent real differences in efficacy rather than differences in patient selection, clinical evaluation, and other factors, since these factors will be handled in similar fashion for both arms of the study. The purpose of randomized phase II designs is not a formal, rigorous comparison of two or more treatment arms, but rather a reduction in certain sources of variability that afflict conventional phase II trials and their comparison across studies. Moreover, this design offers the additional advantage, that the trial may immediately be expanded into a phase III trial including the patients already randomized, if the results of the experimental group(s) are considered to be promising.

8.3.4 Design and assumptions

- Explorative randomized phase II study with 2 parallel groups.
- Primary endpoint: Overall survival rate after 2 years. Survival time will be calculated from time of randomization until death for any reason, or until last date known to be alive, whichever occurs first. In patients without death, the last date known to be alive will be considered as censored survival time.
- The respective experimental therapy arm would be rated as insufficiently active, if the observed OS rate at 2 years is 40 % or lower, as this corresponds to the standard treatment efficacy.
- On the other hand, the experimental therapy would be considered to be a promising candidate for further development (e.g. in a phase III trial), if the true OS rate at 2 years amounted to 45% or more.

- In order to detect potential differences with respect to the investigated study endpoints between female and male gender, subgroup analyses will be performed for both female and male patients. Furthermore, the potential prognostic impact of gender will be analyzed in a univariate and a multivariate manner. Because an adequate statistical power cannot be expected in each of the two subgroups, the statistical evaluation analyses with respect to gender related differences will be presented in a descriptive manner.

8.4 Sample size calculation

This phase II study is an explorative randomized study with 2 parallel groups. Using a standard single-stage phase II design by FLEMING (1981), $n = 62$ patients evaluable for efficacy have to be recruited. As a similar number of patients is to be recruited to the standard arm, a total number of 124 patients is required. The standard treatment control group serves to reduce some of the result variability which is typically encountered in single-arm phase II trials, especially caused by patient selection phenomena and investigator bias. To cover potentially drop outs 67 patients per arm will be recruited.

The OS rate after 2 years is chosen as primary efficacy endpoint. The estimation of the efficacy rate of 40% of the reference group is based on the findings of several studies [49-54]. Therefore, the respective experimental therapy arm would be rated as insufficiently active, if the observed OS rate at 2 years is 40 % or lower.

On the other hand, the experimental therapy would be considered to be a very promising candidate for further development (e.g. in a phase III trial), if the true OS rate at 2 years amounted to 45 % or more.

Probability to accept the experimental therapy as promising ($> 45\%$ OS rate) with respect to efficacy, in spite of a true OS rate of $\leq 40\%$: 5% (type I error).

Probability to reject the experimental therapy as not sufficiently efficient ($\leq 40\%$), although the true OS rate is promising ($> 45\%$): 20% (type II error, corresponding to a power of 80%).

However, the last patient will be randomized on December 31, 2016 at the latest, which is 2.5 years later than originally planned. Based on number of patients randomized until end of July and who received study treatment ($n=66$) it is expected that the total number of patients in the Full Analysis Set (FAS) will be between 72 and 78 patients, while the number of patients in the Per Protocol Population is expected to be between 66 and 72 patients.

The final conclusion of the phase II trial will depend on the definite OS rate (and its confidence interval), the respective findings in the 5-FU/cisplatin reference arm, as well as the information on type, frequency and severity of toxicities.

The 2-years overall survival rates will be estimated using Kaplan-Meier methods and the difference between treatment groups regarding 2-years overall survival curves will be compared using the log-rank test. In addition, univariate Cox proportional hazard methods will be used to estimate the corresponding hazard ratio (HR) and 95% confidence intervals for HR.

Based on the expected number of patients randomized until end of 2016, the following difference (hazard ratios) can be detected between the two treatment arms with 80% power and a two-sided significance level of 0.05, assuming that the 2-years OS probability is between 30 and 40%, and number of lost-to-follow-ups is about 5% during the 2 years.

Table 10: Hazard ratios and necessary numbers of events

Sample size	2-year OS probability		Necessary number of events	Hazard ratio
	CT only	CT plus Cetuximab		
2 x 33	30%	63.14	34	0.3820
	35%	68.38	31	0.3621
	40%	73.19	28	0.3407
2 x 36	30%	61.73	38	0.4007
	35%	67.02	35	0.3812
	40%	71.90	31	0.3601
2 x 39	30%	60.48	42	0.4177
	35%	65.81	38	0.3986
	40%	70.74	34	0.3778

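### No observed cut-off that the text suggests for the cetuximab arm's 2-year survival meets the stated 5% type I error, and the weight of the randomised control in the verdict is not defined

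*Combined protocol and SAP*

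**What the plan says.** Section 8.3.2 cites an "overall survival (OS) rate of 36% to 40% after two years" for the best 5-FU/cisplatin regimens, and concludes that "a 40% OS rate at 2 years is assumed as the baseline efficacy level for the present trial". Section 8.3.4 rates the experimental arm insufficiently active "if the observed OS rate at 2 years is 40 % or lower, as this corresponds to the standard treatment efficacy". Section 8.4 and the synopsis repeat this: the arm "would be rated as insufficiently active, if the observed OS rate at 2 years is 40 % or lower". The regimen is promising "if the true OS rate at 2 years amounted to 45 % or more".

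Section 8.4 then gives two error rates. A 5% type I error is attached to accepting the regimen as promising (above 45%) when the true rate is 40% or less. A 20% type II error is attached to rejecting it (40% or less) when the true rate exceeds 45%. The sidedness of the 5% is not stated. The design is a single-stage Fleming design with 62 evaluable patients in the experimental arm; the expected totals are now 66-72 (per protocol) and 72-78 (full analysis set).

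On the control arm, Section 8.3.3 says "The purpose of randomized phase II designs is not a formal, rigorous comparison of two or more treatment arms". Section 8.4 makes the final conclusion depend on the survival rate and its confidence interval, the reference-arm findings and toxicity. It adds that "the difference between treatment groups regarding 2-years overall survival curves will be compared using the log-rank test", with a Cox hazard ratio and 95% CI. Table 10 gives detectable hazard ratios at two-sided 0.05 and 80% power.

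**The concern.** A cut-off on the observed rate placed at the null value is exceeded about half the time when the null is true. The other level, 45%, refers to a quantity that nobody will observe. A reader therefore cannot tell what result counts as acceptance, and the 5% has no stated cut-off to which it belongs.

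The threshold also judges one arm against history, in a trial randomised to limit patient-selection effects. Section 8.4 itself allows 2-year survival of 30% to 40% when computing Table 10. If the enrolled patients differ from the historical series, the position relative to 40% reflects case mix as well as treatment. The plan does not say what happens if the threshold and the between-arm comparison disagree. Section 8.3.3 raises the possibility of expanding into phase III on promising results, so the verdict has consequences.

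**Working it through.** **Inputs.** Null rate 40% (8.3.2); promising rate 45%, type I error 5%, type II error 20%, n = 62 (8.4). Expected sizes are 33-36 per arm (per protocol) and 36-39 (full analysis set), from the totals in 8.4 with an equal split, which is an assumption.

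**1. The plan's own figure.** The one-sample normal formula, one-sided, is

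n = [(1.645·√(0.40·0.60) + 0.842·√(0.45·0.55)) / 0.05]² ≈ 600.

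The exact binomial search gives 604 and the two-sided formula 761. The stated 62 is not reproduced, so the next step asks what errors a cut-off has at 62.

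**2. Error of each observed cut-off.** With X ~ Binomial(n, 0.40), compute P(X ≥ r), where r is the smallest count above 40% (or above 45%) of n.

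| n | r for >40% | P | r for >45% | P |
|---|---|---|---|---|
| 33 | 14 | 45.3% | 15 | 31.9% |
| 34 | 14 | 50.9% | 16 | 25.1% |
| 35 | 15 | 42.7% | 16 | 30.0% |
| 36 | 15 | 48.2% | 17 | 23.6% |
| 37 | 15 | 53.6% | 17 | 28.2% |
| 38 | 16 | 45.6% | 18 | 22.2% |
| 39 | 16 | 50.9% | 18 | 26.5% |
| 62 | 25 | 52.8% | 28 | 24.1% |

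Subtracting the two probabilities gives the chance of a result with no verdict: about 13-26% at 33-39 per arm and 52.8 − 24.1 = 28.7% at 62.

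**3. The stated type II error.** At n = 62 and a true 45%, P(X ≥ 25) = 80.7%, so an observed rate of 40% or less has probability 19.3%. This fits the stated 20%. The same cut-off has a 52.8% false-positive risk. At 33-39 per arm the corresponding type II error is about 24-34% (for example 1 − 0.680 = 32.0% at 33 and 1 − 0.744 = 25.6% at 39).

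**4. Cut-offs that do hold 5% one-sided.**

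| Cut-off | Observed rate | Type I error | Power at true 45% |
|---|---|---|---|
| ≥19/33 | 57.6% | 3.1% | 10% |
| ≥20/36 | 55.6% | 4.3% | 13% |
| ≥22/39 | 56.4% | 2.8% | 10% |
| ≥32/62 | 51.6% | 4.2% | 18% |

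**5. Sensitivity.** Replacing the binomial count by a Kaplan-Meier estimate (exponential survival, 5% loss, simulated) puts the >40% figure at 49-50% at n = 33, 36, 39, 62 and 67. With a true rate of 36%, the low end in 8.3.2, the binomial figure is 25-34% at 33-39 and 27.9% at 62.

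**6. Dependence on case mix (illustrative true rates).** If both arms truly had 50%, an assumption not in the documents, an inert regimen would exceed 40% in 85.2% (n = 33) to 87.9% (n = 36) of trials. If control were 30% and cetuximab raised it to 40% (HR = ln 0.40 / ln 0.30 = 0.76), the arm would be rated insufficiently active in 54.7% (n = 33) or 51.8% (n = 36).

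**The case against.** The strongest reply is that the threshold is not the whole verdict. Section 8.4 brings in the confidence interval, the reference arm and toxicity, and plans a log-rank test and hazard ratio. This stands. A reader might infer that the randomised control plays no part; the documents do not support that. The control is absent from the 40% and 45% levels, and its weight elsewhere is unspecified.

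A reader might also set 43-54% directly against the stated 5%. Those are different events: the 5% belongs to accepting the regimen as promising, whereas exceeding 40% only avoids the label insufficiently active and triggers no stated action. The closest like-for-like figure reads acceptance as observed above 45%, and gives 22-32%. For the same reason it goes too far to say that an inert drug passes: with equal arms, the planned hazard ratio would be expected to sit near 1.

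Nor does the log-rank test contradict Section 8.3.3. That section describes randomised phase II designs in general, and an exploratory test can coexist with it. What is missing is the label and the order of precedence.

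The match between 19.3% and 20% might suggest how 62 was obtained. It does not prove it: the one-sided normal formula also returns 62 for 30% versus 45%, and the documents show no derivation.

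Finally, the trial is called explorative. That lowers the stakes but does not make a stated error rate correct.

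**Conclusion.** The point holds as a wrong stated figure and an incomplete decision rule. On the most favourable reading (accept above 45%, reject at 40% or less), n = 62 gives a type I error of 24.1% and a type II error of 19.3%: the second agrees with the plan, the first is nearly five times the stated 5%. At the expected 33-39 per arm the type I error is about 22-32%. If exceeding 40% is taken as acceptance, it is about 43-54%, and 52.8% at n = 62. Results between 40% and 45% have no verdict, and nothing says whether the threshold or the between-arm result prevails.

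These figures assume a true rate of exactly 40%, an equal split and a binomial count. A lower true rate reduces them, but at 36% the >40% figure is still 25-34% at 33-39 per arm.

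**What to change.** In 8.3.4, 8.4 and the synopsis:

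1. State which observed result counts as promising, and what follows between 40% and 45%. Replace the 5% with the real error of that cut-off at the expected size: about 22-32% for above 45%, about 43-54% for above 40%, naming the event in each case.
2. State that the interpretation of efficacy rests mainly on the randomised contrast: the planned hazard ratio with 95% CI, plus the difference in Kaplan-Meier 2-year survival with 95% CI. Make the comparison with 40% descriptive.
3. If a fixed cut-off holding 5% one-sided is kept (at least 19/33, 20/36 or 32/62), state that its power at a true 45% is only about 10%, 13% and 18%.
4. Label the log-rank test exploratory, so that it agrees with 8.3.3.

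No new data are needed. The cost is in what the plan can claim: the stated error or power becomes much less favourable, and the contrast will have a wide interval. Table 10 reaches 80% power only for hazard ratios of about 0.34-0.42. For 45% against 40% (HR = ln 0.45 / ln 0.40 = 0.87), the 38-45 events expected with 33-39 per arm, from n × (0.60 + 0.55), give about 6-7% power at two-sided 0.05.

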
Sample size calculation and explanation
	
This is an explorative randomized study with 2 parallel groups. Using a standard single-stage phase II design by FLEMING (1981), n = 62 patients evaluable for efficacy have to be recruited. As a similar number of patients is to be recruited to the standard arm, a total number of 124 patients is required. The standard treatment control group serves to reduce some of the result variability which is typically encountered in single-arm phase II trials, especially caused by patient selection phenomena and investigator bias. To cover potentially drop outs 67 patients per arm will be recruited.
 
The OS rate after 2 years is chosen as primary efficacy endpoint. The estimation of the efficacy rate of 40% of the reference group is based on the findings of several studies (Bedenne 2007, Herskovic 1992, Minsky 2002, Stahl 2005, Al-Sarraf 1997, Cooper 1999). Therefore, the respective experimental therapy arm would be rated as insufficiently active, if the observed OS rate at 2 years is 40 % or lower.
 
On the other hand, the experimental therapy would be considered to be a very promising candidate for further development (e.g. in a phase III trial), if the true OS rate at 2 years amounted to 45 % or more.
 
Probability to accept the experimental therapy as promising (> 45% OS rate) with respect to efficacy, in spite of a true OS rate of $\leq 40\%$: 5% (type I error).
 
Probability to reject the experimental therapy as not sufficiently efficient ($\leq 40\%$), although the true OS rate is promising (> 45%): 20% (type II error, corresponding to a power of 80%).
 
The final conclusion of this trial will depend on the definite OS rate (and its confidence interval), the respective findings in the 5-FU/cisplatin reference arm, as well as the information on type, frequency and severity of toxicities.

End of the study
	
The end of study is reached when the last patient has completed the 2-year Follow-up period.

[figure not shown]
Schedule of Assessments

Evaluation	Screening		Radio-immunochemotherapy				Follow-Up (every 3 month) ⁸
	Day -28 to 0	Day -7 to 0	weekly	every 4 weeks	after 4-4.5 weeks	End of Treatment	
Written informed consent	X						
Medical history	X						
Clinical staging (endoscopy incl. biopsy)	X				X	X	
Endoscopic ultrasound	X				X	X	X
Tumor assessment (CT chest, CT abdomen)	X				X	X	X
(Re)-evaluation by a surgeon with respect to resectability	X				X		

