8.1 Analysis set descriptions

Safety Analysis Set

The safety population includes all patients who received at least one dose of trial medication and for whom at least one post-baseline safety measurement is available.

Full Analysis Set

The Full Analysis Set includes all patients who received at least one dose of trial medication and for whom at least one post-baseline efficacy measurement is available.

Per Protocol Set

This population includes all patients with at least six weeks of trial medication plus all patients who discontinued the study prematurely due to lack of efficacy, death or toxicity. Detailed criteria will be defined before analysis.

All safety analyses will be performed on the Safety Analysis Set. For efficacy analysis of the trial, the primary analyses will be based on the per-protocol set. Additional analyses will be performed on the Full Analysis Set for sensitivity purposes.

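### 62 patients do not give 5% type I error and 80% power for a 2-year survival of 45% against 40%; about 600 would be needed, and power is 17.9% at 62 and 10.1–13.5% at the 33–36 per arm now expected

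*Combined protocol and SAP*

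**What the plan says.** The synopsis (sample size row) and section 8.4 give the same basis for the size: "Using a standard single-stage phase II design by FLEMING (1981), n = 62 patients evaluable for efficacy have to be recruited". A similar number goes to the standard arm, so "a total number of 124 patients is required", raised to 67 per arm to cover drop-outs.

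The null rate is fixed in section 8.3.2, where "a 40% OS rate at 2 years is assumed as the baseline efficacy level for the present trial". The target appears in section 8.3.4: the regimen is promising "if the true OS rate at 2 years amounted to 45% or more". The error rates are then attached to these two rates. The type I error is described as "Probability to accept the experimental therapy as promising (> 45% OS rate) with respect to efficacy" when the true rate is at most 40%, and is put at 5%. The probability of wrongly rejecting the regimen is put at "20% (type II error, corresponding to a power of 80"%.

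The current text of section 8.4 also reports the shortfall in recruitment: "the number of patients in the Per Protocol Population is expected to be between 66 and 72 patients". Section 8.1 makes this the set that counts for efficacy: "the primary analyses will be based on the per-protocol set". The synopsis gives 33–36 patients per arm.

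**The concern.** A single-arm test that must separate two rates only 5 percentage points apart, near the middle of the scale, needs several hundred patients. A figure of 62 is too small by about a factor of ten, so at least one of the stated inputs cannot be the one used.

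This calculation is the plan's only quantitative basis for the original size (62, 124, 67 per arm and 134), and it concerns the primary endpoint. The synopsis repeats the 80% figure without Table 10. A reader relying on it would take a result near 40% as good evidence against a 5-point gain, although the trial has little chance of detecting such a gain.

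**Working it through.** **Inputs.** Null rate p0 = 0.40 (section 8.3.2); target p1 = 0.45 (sections 8.3.4 and 8.4); type I error 5%, power 80%, n = 62 (section 8.4 and synopsis). Sidedness is not stated for the Fleming calculation; only Table 10 is declared two-sided. I take one-sided as the main reading because it favours the plan.

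**Attempt to reproduce 62.** One-sample normal formula:

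n = [(z_α·√(p0(1−p0)) + z_β·√(p1(1−p1))) / (p1−p0)]²

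- One-sided: [(1.645·√0.24 + 0.842·√0.2475)/0.05]² = [(0.806 + 0.419)/0.05]² ≈ 600.
- Two-sided (1.960 in place of 1.645): 760.5, so 761.
- Exact binomial, one-sided: both conditions are first met at n = 604 (cut-off 262, α 4.96%, power 80.01%). Because the binomial is discrete, power dips below 80% again just above this and stays at or above it from n = 634 (checked up to 759).
- Continuity correction (620), the arcsine formula (604), swapping the two error rates (606) and a one-sided α of 10% (439) or 20% (277) do not come near 62.

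**What 62 patients give.** Exact binomial, accepting if at least r patients survive 2 years:

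| r of 62 | α at 40% | power at 45% |
|---|---|---|
| 25 | 52.75% | 80.69% |
| 26 | 42.48% | 72.89% |
| 28 | 24.07% | 53.89% |
| 30 | 11.21% | 34.03% |
| 31 | 7.08% | 25.28% |
| 32 | 4.23% | 17.89% |
| 33 | 2.39% | 12.03% |

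No row has α ≤ 5% together with power ≥ 80%. The first cut-off that respects 5% is 32, with 17.9% power. The first that gives 80% power going down the scale is 25, with α above one half.

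**What the expected size gives.** The per-protocol total of 66–72, split equally (an assumption that agrees with the synopsis), is 33–36 per arm. One-sided exact α of at most 5% against 40%:

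| n | cut-off | α | power at 45% | true rate giving 80% power |
|---|---|---|---|---|
| 62 | 32 | 4.2% | 17.9% | 56.1% |
| 33 | 19 | 3.1% | 10.1% | 63.1% |
| 34 | 19 | 4.4% | 13.5% | 61.4% |
| 35 | 20 | 3.0% | 10.2% | 62.6% |
| 36 | 20 | 4.3% | 13.5% | 61.0% |

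**Sensitivity.**

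- Full Analysis Set, 72–78 patients or 36–39 per arm: 10.2–13.5%.
- Originally planned 67 per arm, all evaluable: 20.5%.
- Upper-tail α of 2.5% (two-sided 5%): 12.0% at n = 62 and 5.2–7.5% at n = 33–36.
- Normal approximation, without discreteness: 20.4% at n = 62, 14.9% at n = 33 and 15.5% at n = 36.

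**Inputs that would give about 62.** By the same one-sided formula, 40% against 55.5% gives 62.4 and 30% against 45% gives 61.1, rounded up to 62. This is back-solving; the documents do not say where 62 came from.

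**The case against.** Four points deserve an answer.

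*The literal rule has two thresholds.* The plan rejects the regimen when observed survival is 40% or lower and calls it promising above 45%. At n = 62, rejecting means at most 24 survivors, and the chance of that at a true 45% is 100% − 80.7% = 19.3%, close to the stated 20%. This is right as far as it goes. On the same reading, accepting means at least 28 survivors, and the chance of that at a true 40% is 24.1%, not 5%. The pair still fails, only on the other error rate, and a standard single-stage Fleming design has one cut-off.

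*The trial is exploratory.* Section 8.3.3 disclaims a formal comparison of arms, and section 8.4 rests the conclusion on the survival rate with its confidence interval, the reference arm and toxicity. This limits the damage. But the Fleming claim is a one-arm test against 40%, not a comparison of arms. The interval does not help either: at 33–36 patients, uncensored, its 95% half-width around 45% is 1.96·√(0.2475/33) = 17.0 to 1.96·√(0.2475/36) = 16.3 points.

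*Table 10 already deals with the reduced size.* A reader of section 8.4 does learn from it that only large effects are detectable: 60.48–73.19% with cetuximab against 30–40% without. But it is a two-arm, two-sided log-rank calculation. It neither supports nor withdraws the 5%/80% statement, which stands uncorrected in the same section, and the synopsis omits it. Sections 4.1, 8 and 8.4 do follow the original targets with the recruitment stop; the synopsis sample size row does not.

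*The exact binomial is only a proxy.* The planned analysis is Kaplan–Meier with log-rank and Cox, and part of the 10.1–13.5% range is discreteness. Both are true. The smoother normal figures of about 15% lead to the same conclusion, and censoring would remove information, not add it.

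**Conclusion.** The concern holds. The stated 5% type I error and 80% power for 45% against 40% are not properties of a design with 62 patients. The requirement is about ten times larger (about 600 one-sided, 761 two-sided). Exact power at 45% is 17.9% at the planned 62 and 10.1–13.5% at the 33–36 per arm now expected in the primary analysis set.

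These figures assume a one-sided 5% test, an equal split of the per-protocol set and known 2-year status for every patient. A two-sided test makes the gap larger. The practical consequence is limited by the exploratory aim and by Table 10, but the statement is wrong as written in both places and should be corrected. The documents do not show which input was wrong.

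**What to change.** In section 8.4 and the synopsis:

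1. Retrieve the dated original calculation and state which input was wrong. Do not choose a target rate now so that 62 comes out.
2. Delete the statement that 62 patients give 5% and 80% for 45% against 40%.
3. State what the trial can do, as a description and not as a decision rule. For example: *With 33–36 evaluable patients in arm A and a one-sided exact type I error of at most 5% against 40%, power is about 10–13.5% if the true 2-year survival is 45% and reaches 80% only at about 61–63%; the trial is unlikely to distinguish 45% from 40%.*
4. Give the corrected basis for 62, 124, 67 per arm and 134, or mark them as original targets that are no longer expected. The synopsis sample size row needs this most.
5. Carry Table 10's reduced-size sensitivity into the synopsis.

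The cost is a wording change in two places and one look-up. No patients, analyses or decision thresholds change; the stated sensitivity of the trial becomes less favourable.
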